4.6.1. General Method

This study will be conducted by including children between the ages of 4-11 who apply to the Department of Pedodontics, Faculty of Dentistry, Necmettin Erbakan University, and who do not have any systemic diseases. The required number of participants was obtained after power analysis based on the data of a previously conducted study on the subject [$\alpha=0.05$, $\beta=0.05$ and $\text{power}=0.95$]. Considering that 60 people should be included in the study and the possibility of loss, the sample size was determined as 90.¹⁴

Patients who apply to the Department of Pedodontics, Faculty of Dentistry, Necmettin Erbakan University, meet the inclusion criteria and will be offered to participate in the study if they give their consent to the informed consent form.

The study and control groups will be determined randomly in order to eliminate variables that may cause differences in patients over time. Randomization will be done through the website "randomizer.org". Before starting the study, patients and their parents will be informed about the treatment procedure to be applied.

Systemic and dental history will be taken from the patients before starting the extraction procedure. After clinical examination with inspection, palpation and percussion, periodontal and radiographic examination will be performed. Patients who meet the inclusion criteria will be informed about the study and their written informed consent will be obtained. Since gender is one of the factors that can affect postoperative pain, female and male patients will be distributed equally. Postoperative pain will be assessed using the Wong Baker Pain Rating Scale, where the patient can mark the pain level after the anesthesia procedure. The FLACC test will be evaluated with the video taken during the anesthesia procedure. Later, statistical evaluations and comparisons between groups will be made.

4.6.1. Components of a Study-Specific Clinical Assessment:

Sociodemographic form: This is a sociodemographic information form prepared by the researchers that includes information such as age, gender, contact information, and medical condition of the patients.

Tooth-material information form: This is a form prepared by the researchers that records which teeth were included in the study and the file system used on the teeth.

FLACC Scale: This is the form where the pain status is recorded using the FLACC scale at the end of the procedure for the teeth included in the study prepared by the researchers. This scale will be evaluated by looking at the video recording taken during palatal anesthesia of the upper primary molar teeth that need to be extracted. The tooth will be extracted after anesthesia.

Wong Baker Pain Rating Scale: This is a form that records the pain status of the teeth included in the study, prepared by the researchers, using the Wong Baker Pain Scale at the end of the procedure. This scale will be used immediately after the palatal anesthesia of the upper primary molars that need to be extracted. The tooth will be extracted after anesthesia.

Dental Anxiety and Fear Index (IDAF-4C): The four components covered by the measure include

emotional, behavioral, physiological, and cognitive modules, and a basic fear module.15 This index will be administered to the patient before anesthesia. After anesthesia, the tooth will be extracted.

4.7. 4.7. Evaluation of Data:

The data obtained as a result of our study will be evaluated with the help of SPSS package program. Postoperative pain will be evaluated using Wong Baker Pain Rating Scale, where the patient can mark the pain status after the anesthesia procedure. FLACC test will be evaluated with the video taken during the anesthesia procedure. The obtained data will be evaluated with descriptive and explanatory statistics with the help of SPSS package program. Anova test and Post Hoc Tukey test will be used for comparison between groups, and independent two-group t test will be used to evaluate the pain status between male and female patients within the groups.

RESOURCES:

- 1-Önçağ Ö., & Çoğulu D. Ailenin Sosyoekonomik Durumu ve Eğitim Düzeyinin Çocuklarda Dental Kaygı Üzerine Etkisi.
- 2-Kleinknecht R. A., Klepac R. K., & Alexander L. D. (1973). Origins and characteristics of fear of dentistry. The Journal of the American Dental Association, 86(4), 842- 848.
- 3-Yardımcı S. (2018). Çocuklarda İnfiltratif Anestezi Yöntemi ile Tek Diş Anestezi (STA) Tekniğinin Karşılaştırılması. (Doktora tezi), İstanbul Üniversitesi.
- 4-<http://www.comfort-inturkiye.com/dis-hekimligi-2/>. (2020). Comfort-in İğnesiz Enjektor Türkiye Resmi Sayfası. from <http://www.comfort-inturkiye.com/dishekimligi-2/>

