RESEARCH PROTOCOL**1. PROJECT NAME:**

Clinical Evaluation and Comparison of Pain Acceptance of Different Types of Injection Systems in Palatal Anesthesia Applied to Children

2. JUSTIFICATION OF THE PROJECT:

Dental anxiety and fear are very common in the pediatric population. In order to cope with this feeling, the dentist must have knowledge about the degree of anxiety in children, its etiology and the child's psychology.¹ One of the most widely known and important factors in the development of dental anxiety or fear is "painful dental treatments". The child's encounter with a painful procedure just once or even the feeling that they will feel pain is enough to cause anxiety and fear. A friendly relationship with the dentist helps patients cope with specific stimuli known to cause anxiety and fear, such as anesthesia, the sound and sight of the aerator.² Local anesthesia is the blocking of pain sensation by applying a drug topically or by injection to a part of the body without affecting the level of consciousness. Preventing pain sensation during dental procedures can increase the relationship between the patient and the dentist, develop trust, alleviate fear and anxiety, and enable the patient to have a positive attitude towards dental procedures.³

Traditional local anesthesia application methods can cause increased dental anxiety in children. Therefore, new needle-free and painless local anesthesia techniques are being developed in parallel with technological developments. With the development of needle-free injection systems, the patient's needle phobia and the resulting dental anxiety are prevented. Jet injection systems, computer-controlled local anesthesia injection systems, electronic dental anesthesia, vibration systems, laser analgesia, virtual reality anesthesia and iontophoresis are needle-free injection methods. The Comfort-in jet injection system is a device that injects the anesthetic solution with pressure in a short time.⁴

There are many studies on various anesthetic agents used during operations, different anesthesia, and different analgesic, anti-inflammatory and immunosuppressive agents used after the operation, in order to ensure that patients tolerate this surgical procedure more easily, feel less pain, and go through this period more easily and without problems, both during and after the operation.

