The groups will be formed according to the split mouth method in the same patient with symmetrical primary molar teeth. In all groups, "Ultrave D-S Forte 80 mg + 0.03638 mg/ 2 mL (Articaine hydrochloride Epinephrine bitartrate)" will be used as a local anesthetic. In the study group, teeth will be extracted using Comfort-In™ Needle-Free Injection with a single point palatal injection. In the control group, teeth will be extracted using a single point standard injection. Parents of patients who are considered to participate in the study will have their consent forms filled out and a previously prepared informed consent form will be obtained. Children who have planned extraction treatment for maxillary primary molars, have symmetrical teeth, do not have any systemic disease, and whose parents can give consent will be included in the study. Necessary anesthesia will be applied before the extraction procedure and the tooth will be extracted. In patients who are anesthetized with Comfort-In™ Needle-Free Injection during the procedure, if they feel serious pain, the procedure will not be continued and the patient will be excluded from the study. After the anesthesia procedure, the patient will be able to mark the pain level using the Wong Baker Pain Rating Scale. The FLACC test will be evaluated with the video taken during the anesthesia procedure. The obtained data will be evaluated with descriptive and explanatory statistics using the SPSS package program. Anova test and Post Hoc Tukey test will be used for comparison between groups, and an independent two-group t test will be used to evaluate the pain level between male and female patients within groups.

In the volunteer group to which the drug is applied with the "Comfort-in Needle Injection", if the anesthesia procedure is insufficient and/or does not occur, the patient will be given the traditional injection method as a rescue treatment and the patient will be excluded from the study, but the treatment will continue.

A guarantee will be given that the personal data collected will be collected and processed in accordance with the Personal Data Protection Law No. 6698, will not be used or shared for any purpose other than the purpose of collection/processing, that the data will be destroyed when the volunteer withdraws his/her consent, the research ends or the processing of personal data ends, and that the collected personal data will not be shared.

4.1. Location of the Research:

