Children aged 4-11 years who do not have any systemic disease and who apply to the Department of Pedodontics of Necmettin Erbakan University Faculty of Dentistry are planned to be included in our study.

4.2. Time of the Research:

It is planned to be held between 01.02.2024 - 01.08.2024.

4.3. Research Universe, Sample, Research Group:

Children between the ages of 4 and 11 who apply to the Department of Pedodontics, Faculty of Dentistry, Necmettin Erbakan University, and who do not have any systemic diseases will be included in our study. The groups will be formed according to the split mouth method, with symmetrical primary molar teeth in the same patient. Teeth in the study group will be extracted with Comfort-In™ Needle-Free Injection. Standard injection will be applied for teeth extraction in the control group.

Inclusion criteria for the study;

Patients;

- Between the ages of 4-11
- Bilateral maxillary primary molars with an indication for extraction
- Have not taken any analgesics up to 12 hours before treatment
- Have not used antibiotics in the last month
- Teeth with no more than 1/2 of the root physiologically resorbed
- Systematically healthy children
- Those who agree to participate in the study
- Must show a score of 3-4 or 1-2 according to the Frankle Behavior Scale
- Frankle 1: Patients who refuse treatment, cry, are excessively anxious or show signs of severe negative behavior
- Frankle 2: Patients who are non-compliant, unwilling to treat, show vague signs of negative behavior, are sullen but do not express anxiety
- Frankle 3: Patients who accept treatment, are compliant, shy, establish a relationship with the physician but approach it in a measured manner
- Frankle 4: Patients who cooperate with the physician, are curious about treatment, smile and are happy with the environment Frankle(1962)

Teeth;

- Bilateral maxillary primary molars with extraction indication

4.4. Type of Research:

Prospective, experimental, randomized clinical trial

4.5. Manpower Required for Research:

Assistant [name] [name] (Project manager, creation of research design, clinical evaluation, data analysis and study writing)

Dt. [name] (Assistant researcher, routine patient follow-up, application of extraction treatment, data analysis and study writing)

4.6. Data Collection Tools of the Research:

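### The split-mouth trial states an ANOVA with Tukey between groups, which ignores that both teeth belong to one child; the randomisation text also leaves unsaid which system is given first

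*Protocol*

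**What the plan says.** **Design.** Section 4 (Materials and Methods) of the Protocol states: "The groups will be formed according to the split mouth method in the same patient". Section 4.3 repeats it ("with symmetrical primary molar teeth in the same patient"), and its inclusion criteria require molars for extraction on both sides. Each child is therefore due one injection with Comfort-In and one standard injection. Section 2.2.3 confirms that two systems are compared.

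**Analysis.** Sections 4 and 4.7 both say: "Anova test and Post Hoc Tukey test will be used for comparison between groups". Neither mentions a paired test, repeated measures or a term for the child.

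**Randomisation.** Section 4.6.1 (General Method) says: "The study and control groups will be determined randomly in order to eliminate variables that may cause differences in patients over time". It adds "Randomization will be done through the website" and names the site. It does not say whether the list allocates the side, the sequence, or both.

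**Outcome timing and form.** Section 4.6.1 (Components) has Wong-Baker completed straight after the palatal injection and FLACC scored from video of it. The tooth form in the same section "records which teeth were included in the study and the file system used on the teeth". No files are used in this trial, so that field looks like a wording error.

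**The concern.** Two scores from one child share that child's anxiety, age and way of using the scale, so they are likely to be positively correlated. A split-mouth design is chosen because taking the difference within a child removes this shared part. An independent-groups ANOVA leaves it in the error term and so gives up the design's main advantage. Because the protocol states a method that does not fit its own design, this is a contradiction and not a detail left to a statistical analysis plan.

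The second matter is sequence. One injection precedes the other, and both outcomes are taken at the injection. Section 2 itself argues that a child's "encounter with a painful procedure just once or even the feeling that they will feel pain is enough to cause anxiety and fear", so the first experience may well colour the second score. Allocating sides at random does not by itself fix which system goes first. If nearly all children had the same order, no later analysis could separate order from device.

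**Working it through.** **Inputs from the Protocol:** two systems, both in the same child; 60 needed, 90 recruited; alpha 0.05, power 0.95.
**Assumptions:** within-child correlation ρ = 0.3 or 0.5; equal variances; two-sided 5% tests; 60 complete pairs; first-versus-second effect d = 0.1 or 0.3 SD of the within-child difference. The Protocol gives none of these.

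**The plan's own figure.** The 60 cannot be reproduced, because no effect size, SD, test or sidedness is given. With 1.960 + 1.645 = 3.605, it fits 30 per independent group at 3.605 × √(2/30) = 0.93 SD, 60 per group at 3.605 × √(2/60) = 0.66 SD, or 60 pairs at 3.605/√60 = 0.47 SD of the difference. The document does not say which.

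**Pairing**
1. With n pairs and unit variance, the true variance of the mean difference is 2(1−ρ)/n. The independent-groups ANOVA uses about 2/n.
2. Interval width relative to the correct one is 1/√(1−ρ): 1.20 at ρ = 0.3 and 1.41 at ρ = 0.5.
3. True type I error ≈ 2[1 − Φ(1.960/√(1−ρ))]. At ρ = 0.3, 1.960/0.837 = 2.343, giving 0.019. At ρ = 0.5, 1.960/0.707 = 2.772, giving 0.006. Simulation agrees.
4. Power. A paired t test with 60 pairs has 95% power at 0.473 SD of the difference (t-based), and 0.473 × √60 = 3.665. For the unpaired test, power ≈ Φ(3.665 − 2.343) = 0.91 and Φ(3.665 − 2.772) = 0.81. Simulation with t quantiles gives 0.90 and 0.80.
5. Two-group ANOVA is the two-sample t test, so with one contrast Tukey has nothing to adjust.

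**Order**
1. Let s be the share of children given one particular system first. Bias in the device difference = s·d − (1−s)·d = (2s−1)·d.
2. For d = 0.1 to 0.3 SD, the bias is 0 at s = 50%, 0.02–0.06 SD at 60%, 0.06–0.18 SD at 80% and 0.10–0.30 SD at 100%.
3. False positives under the stated unpaired test, no true device difference:

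| Share in one order | d (SD) | ρ = 0.3 | ρ = 0.5 |
|---|---|---|---|
| 60% | 0.3 | about 3% | about 1% |
| 80% | 0.3 | about 17% | about 8% |
| 100% | 0.1 | about 6% | about 2% |
| 100% | 0.3 | about 49% | about 32% |

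Check of the last row: 0.3 × √60 = 2.324; Φ(2.324 − 2.343) = 0.49 and Φ(2.324 − 2.772) = 0.33, close to the simulated values.

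**The case against.** **On pairing.** ANOVA could mean a repeated-measures form, and the error, if made, is on the safe side. The first is possible, but a between-groups comparison with Tukey and no term for the child does not read that way. The second is correct: a reader might infer that ignoring the pairing produces false positives, and with positive correlation it does the opposite. A reader might also infer that the trial falls short of its planned 95% power. The Protocol does not support that: the 60 may have been derived for independent groups, in which case this ANOVA would deliver the planned power. The 90% and 80% hold only relative to a paired test on the same children.

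**On order.** The randomisation sentence gives differences over time as its purpose, which fits sequence at least as well as side, and treating the sides in a fixed sequence would make device order random too. That stands: order may have been intended. A reader might infer that one system will in fact usually come first. No passage says so. What remains is that no stated step secures the purpose, and the plan could be followed exactly with a lopsided order.

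**Interaction.** The conservative test partly masks an order bias, so false positives stay near or below 5% unless imbalance is strong and the effect large. The bias in the estimate is unchanged.

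**Smaller points.** The mention of a file system does not show that order goes unrecorded. Nor will every child supply a complete pair: after serious pain with Comfort-In, section 4 says "the procedure will not be continued and the patient will be excluded from the study", and it also excludes children after insufficient anaesthesia with that system.

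**Conclusion.** The analysis point holds as the text stands: a within-child design is paired with a between-groups test. The consequence is lost precision and power, not bias. How much is lost depends on a within-child correlation that the document does not give; at zero correlation nothing would be lost.

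The order point holds in a weaker form: the randomised unit is not named, and order is not secured by any stated step. The size and direction of a first-versus-second effect are unknown, so the order figures are illustrations. A mild imbalance does little; a near-fixed order could shift the device difference by the whole order effect. Both points should be corrected, and the order point must be settled before the first child is treated, since analysis cannot repair a fixed order afterwards.

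**What to change.** - **Sections 4 and 4.7:** replace ANOVA and Tukey with a within-child comparison of the two systems, either a paired test or a mixed model with child as random effect. Order may be added as a fixed effect.
- **Section 4.6.1 (General Method):** state that for each child the randomizer.org list assigns, 1:1, which system is given first as well as which side receives which system. If this was already intended, one sentence settles it.
- **Tooth form, section 4.6.1 (Components):** replace the file-system field with injection system, side, and order (first or second).

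Cost: a different list from the same website, one corrected form field and slightly more analysis work. No extra patients or visits are needed.

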2.2.2 FLACC Scale

The FLACC scale was first introduced in 1997. This scale scores behavioral characteristics consisting of 5 categories. It reminds us of scoring with initials; F: Face, L: Legs, A: Activity, C: Cry, C: Consolability. Each category is scored between 0 and 2. The highest value is 10. Total score; 0: Calm and comfortable, 1-3: Mild discomfort, 4-6: Moderate pain, 7-10: Can be evaluated as severe discomfort or pain or both.¹³

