2.2.3 Complications of Anesthesia

Complications related to the tissue may be observed after anesthesia. These complications are listed below:

- 1- Hematoma
- 2- Pain
- 3- Needle breakage
- 4- Infection
- 5- Emphysema
- 6- Inadequate anesthesia
- 7- Palatal mucosa necrosis

Complications that may be observed after two different anesthesia systems are applied will be recorded.

3. PURPOSE OF THE PROJECT:

3.1. Main Purpose of the Project:

Palatal injection, which is routinely used in the extraction of primary molars, causes pain and fear due to the tight connection between the palatal mucosa and bone, and causes difficulty in tolerating by pediatric patients. The purpose of our study is to evaluate Comfort-In™ Needle-Free Injection in terms of pain perception in children in palatal infiltration anesthesia applied to the upper jaw, which is difficult to tolerate by patients.

4. MATERIALS AND METHODS OF THE RESEARCH:

The required number of participants was obtained after power analysis based on the data of a previously conducted study on the subject [alpha(α)=0.05 beta(β)=0.05 and power=0.95]. Considering that 60 people

should be included in the study and the possibility of loss, the sample size was determined as 90.¹⁴

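### FLACC is scored from video of the injection, but the protocol names no rater, describes no masking of the clips, and does not bar the person who injected from scoring

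*Protocol*

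**What the plan says.** The protocol describes FLACC as five observer-judged categories (section 2.2.2): "Each category is scored between 0 and 2. The highest value is 10". The general method (section 4.6.1) says: "The FLACC test will be evaluated with the video taken during the anesthesia procedure". Sections 4 and 4.7 say the same. The FLACC paragraph under the study-specific assessments repeats it: "This scale will be evaluated by looking at the video recording taken during palatal anesthesia".

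The comparison is within the child (section 4): "The groups will be formed according to the split mouth method in the same patient with symmetrical primary molar teeth". One side receives the needle-free device and the other the standard injection. Section 4.4 gives the design as "Prospective, experimental, randomized clinical trial", and no blinding term appears anywhere in the document.

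Section 4.5 lists two people. The duties of the first are "Project manager, creation of research design, clinical evaluation, data analysis and study writing". Those of the second are "Assistant researcher, routine patient follow-up, application of extraction treatment, data analysis and study writing". Neither entry mentions FLACC scoring or says who gives the injection.

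**The concern.** Face, legs, activity, cry and consolability are judgements, and a rater who knows the device can lean on them without intending to. The protocol's justification (section 2) already presents needle-free systems as a way to prevent needle phobia and the anxiety that follows from it, so an expectation about the direction of the result is on record.

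Randomising which side gets which device does not protect against this, because the shift follows the device and not the side. Pairing does not protect against it either: stable differences between children cancel, but a device-linked shift goes into the mean difference in full. A larger sample only makes the shifted difference look more certain.

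Scoring from a recording is the setting in which some masking can be had cheaply. Who scores, and what they know when they score, is trial conduct that must be settled before the first clip is rated. It cannot be left to a statistical analysis plan.

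**Working it through.** **1. What the document fixes.** Four questions were put to every place where FLACC scoring is mentioned (sections 2.2.2, 4, 4.6.1 and 4.7) and to the staff list in section 4.5.

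| Question | Answer in the protocol |
|---|---|
| Who scores? | Not stated |
| Who gives the injection? | Not stated; section 4.5 assigns only the extraction |
| Are clips coded, shuffled or stripped of labels? | Not stated |
| May the person who injected also score? | Not addressed |

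**2. The plan's own figures.** Sections 4 and 4.6.1 give "alpha(α)=0.05 beta(β)=0.05 and power=0.95", with 60 people needed and 90 planned. No effect size, SD or endpoint is stated, so the 60 cannot be reproduced. The 90 equals 60/(1 − 1/3). These figures serve below only as numbers of pairs.

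**3. Illustration of sensitivity.** The following are assumptions, not document figures: true difference 0; SD of the within-child FLACC difference 2 to 3 points; mean device-linked scoring shift b of 0.25 or 0.5 point on the 0 to 10 scale; two-sided paired t test at 0.05 (the protocol does not state sidedness).

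Non-centrality = b × √n / SD. The false-positive rate is the probability that a non-central t with n − 1 degrees of freedom falls beyond the critical value (2.001 for n = 60, 1.987 for n = 90). For example, with n = 60, b = 0.5 and SD = 2: 0.5 × 7.746 / 2 = 1.936, which gives 0.478.

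| Pairs | Shift | SD 2 | SD 2.5 | SD 3 |
|---|---|---|---|---|
| 60 | 0.25 | 0.159 | 0.119 | 0.097 |
| 60 | 0.5 | 0.478 | 0.332 | 0.246 |
| 90 | 0.25 | 0.217 | 0.155 | 0.122 |
| 90 | 0.5 | 0.650 | 0.467 | 0.346 |

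With no shift the rate is 0.05.

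**4. Dependence on the test.** The protocol names ANOVA with Tukey comparisons and does not say whether the ANOVA is repeated-measures. With two devices, a repeated-measures ANOVA is the paired t test, and the table stands. An ordinary between-group ANOVA ignores the pairing. With within-child correlation ρ, its test statistic is the paired one multiplied by √(1 − ρ). At an assumed ρ of 0.5 the factor is 0.707, so the critical value of 1.98 becomes 1.98/0.707 = 2.80 on the paired scale. For 60 pairs and a 0.5-point shift:

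- SD 2: P(Z > 2.80 − 1.936) = P(Z > 0.86), about 0.19.
- SD 3: P(Z > 2.80 − 1.291) = P(Z > 1.51), about 0.07.

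Simulation gives 0.20 and 0.07. For a 0.25-point shift the same formula gives P(Z > 2.80 − 0.968), about 0.03, and P(Z > 2.80 − 0.645), about 0.02. Both are below the nominal 0.05, because that test is already too conservative for paired data. The estimated device difference is shifted by b whichever test is used.

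**The case against.** The strongest reply is that separation may already be intended. Section 4.5 puts clinical evaluation with one person and the extraction with the other, and the natural reading is that the evaluator does not treat. A reader might infer from the silence that the operator will score, or from the shared data-analysis duty that the operator is likely to. The document supports neither: both people carry that duty, and analysing data is not rating an outcome. What stands is narrower. The protocol does not assign the scoring, does not assign the injection, and does not exclude self-scoring.

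Second, separating roles is not masking. The person listed for clinical evaluation also designed the study and may hold the same expectation. FLACC needs the child's face and cry, while the instrument is at the mouth, so neither tight cropping nor muting is fully available. The device may be evident in many clips. This limits what masking can achieve, but coded clips in random order with locked scores are still better than open scoring.

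Third, the percentages rest on an assumed SD, an assumed shift and a test that the protocol does not name. That is correct. They must not be read as an estimate of bias in this trial, since nothing in the document supports a shift of any particular size.

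Fourth, the reach is limited. Wong-Baker is marked by the child, the stated purpose is children's pain perception, and FLACC is not named as primary. A reader might extend the point to the trial's whole pain comparison. Rater expectation on FLACC does not carry over to the self-report.

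**Conclusion.** The point holds for FLACC alone. Followed as written, the protocol allows its only observer-rated pain outcome to be scored with the device known, possibly by the person who gave the injection. Any device-linked shift that resulted could not be removed afterwards.

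The finding rests on the absence of a stated rater and masking step. It does not show that the operator will score or that bias will occur. The illustration (roughly 10% to 48% false positives with 60 pairs, for shifts of 0.25 to 0.5 point, SD 2 to 3 and a paired test) shows only that a shift well under one FLACC point could matter. Under an ordinary between-group ANOVA, at an assumed correlation of 0.5, the 0.5-point shift gives about 7% to 20%. The change should be made because it is cheap and must come before scoring starts.

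**What to change.** Add to the FLACC paragraph in section 4.6.1:

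- The listed investigator who did not give the injection scores the clips. State who injects, so that this can be checked.
- The other investigator codes the clips, trims them to the injection, and frames them on the child as far as scoring Face and Cry allows.
- Clips are presented in random order across children and sides, without device, side or sequence labels.
- Scores are locked before they are linked to the allocation, and the scorer does not hold the allocation list until then.
- The rater records whether the device could be told from each clip, and this is reported.

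**Cost.** Coding, trimming and shuffling the clips. The video and two investigators are already planned, and sample size and treatment do not change. The document does not say who holds the randomisation list. If the intended scorer holds it, that task has to move to the other investigator. Masking remains partial because the device may be seen or heard, and this should be reported as a limitation.

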The aim of this study is to compare the injection pain experienced during palatal local infiltration anesthesia in patients undergoing maxillary tooth extraction with the Comfort-in jet system, which is a needle-free injection method. In addition, to compare the acceptability of anesthesia provided by the Comfort-in jet injection system in children, to determine their preferences, and to evaluate the effect of anxiety level on the severity of pain felt.

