2.2 Pain Acceptance and Clinical Success Evaluation Criteria

2.2.1 Wong Baker Pain Rating Scale

The Wong-Baker Pain Rating Scale pain scale was developed by Donna Wong and Connie Baker. It can be used from the age of 3. It consists of 6 face shapes that express the pain condition. In a study, it was concluded that the Wong-Baker pain scale was more understandable than the VAS scale in children aged 3-14.¹²

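### Both pain scales stop before the extraction: right for injection pain, but the trial cannot compare anesthetic success between the two devices unless the extraction is also scored

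*Protocol*

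**What the plan says.** **Aim.** The end of Section 2 states: "The aim of this study is to compare the injection pain experienced during palatal local infiltration anesthesia". Section 3.1 says Comfort-In is to be evaluated "in terms of pain perception in children in palatal infiltration anesthesia applied to the upper jaw". The end of Section 2 also names the acceptability of the anesthesia that the device provides.

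**Timing of the scales.** Section 4.6.1 (components of the clinical assessment) says of Wong-Baker: "This scale will be used immediately after the palatal anesthesia of the upper primary molars that need to be extracted. The tooth will be extracted". Of FLACC it says: "This scale will be evaluated by looking at the video recording taken during palatal anesthesia of the upper primary molar teeth that need to be" (the sentence closes on removal of the tooth). In both entries the extraction comes next.

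**Labels.** Sections 4.6.1 (General Method) and 4.7 call the Wong-Baker rating postoperative pain, although both place it after the anesthesia. The form descriptions in 4.6.1 also put both scales at the end of the procedure.

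**Success and failure of anesthesia.** The section that holds the scales is headed "2.2 Pain Acceptance and Clinical Success Evaluation Criteria", but no success criterion follows. Section 2.2.3 lists inadequate anesthesia as item 6 of seven complications and adds: "Complications that may be observed after two different anesthesia systems are applied will be recorded". Section 4 says of the Comfort-In group: "if the anesthesia procedure is insufficient and/or does not occur, the patient will be given the traditional injection method as a rescue treatment". That child is then excluded while treatment continues. Section 4 also excludes Comfort-In children who feel serious pain. Neither rule has a counterpart for the standard injection.

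**The concern.** The injection is given so that a tooth can be removed, and whether it worked shows mainly at the extraction. Nothing is scored then. A reader of the results will still want to know whether the more comfortable injection also anesthetized adequately, and the heading of Section 2.2 suggests that the trial will say. As planned, it would have injection scores, an undefined complication item, and a rescue rule that takes failures out of the study on one side only. The label postoperative pain adds the risk that an injection score is reported as pain after the operation.

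**Working it through.** **1. What each source can show**

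| Source | When | Side | Shows adequacy for extraction? |
|---|---|---|---|
| FLACC (4.6.1) | video of the injection | both | no |
| Wong-Baker (4.6.1) | immediately after the injection | both | no |
| Inadequate anesthesia, item 6 (2.2.3) | not stated | both | in principle, but no criterion |
| Rescue and exclusion (4) | when anesthesia is insufficient | Comfort-In only | the child leaves the study |

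Neither of the two scales covers the extraction. None of the forms described in Section 4.6.1 mentions inadequate anesthesia.

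**2. Two passages that do not fit together**

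Section 2.2.3 records complications, including inadequate anesthesia, for both systems. Section 4 removes a child from the study for that same event, on one side only. If excluded children leave the data set, the Comfort-In failure count falls towards zero by construction, while needle failures stay in.

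**3. Room for exclusions**

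The plan needs 60 and recruits 90, so it tolerates a loss of 1 − 60/90 = 33.3%. The protocol gives no failure rate. At assumed Comfort-In exclusion rates of 10%, 20% and 30%, 90 × rate = 9, 18 and 27 children leave, and 81, 72 and 63 remain. The target of 60 would be met in each case, so a shortfall would not reveal the exclusions.

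The figure of 60 cannot be reproduced, because no effect size, standard deviation or sidedness is stated. This point does not depend on it.

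**4. What a paired success outcome could detect**

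Let pJ and pN be the assumed proportions with inadequate anesthesia on the jet and needle sides, independent within child. The discordant cells are b = pJ(1 − pN) and c = pN(1 − pJ). Power of the two-sided exact McNemar test at 0.05 is the sum over m of P(m discordant pairs; n, b + c) × P(reject given m; probability b/(b + c)).

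| pJ v pN | b | c | n = 60 | n = 90 |
|---|---|---|---|---|
| 30% v 5% | 0.285 | 0.035 | 0.95 | 0.995 |
| 30% v 10% | 0.270 | 0.070 | 0.73 | 0.90 |
| 20% v 5% | 0.190 | 0.040 | 0.62 | 0.84 |
| 15% v 5% | 0.1425 | 0.0425 | 0.33 | 0.53 |
| 10% v 5% | 0.095 | 0.045 | 0.09 | 0.16 |

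Independence is the cautious choice if failures cluster within a child. At 20% v 5%, independence implies that 0.20 × 0.05 = 1% fail on both sides. If 3% do, b = 0.17, c = 0.02, and power rises to 0.74 (60) and 0.92 (90).

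**The case against.** The strongest reply is that the scales do what the protocol asks of them. The aim is injection pain, and a score taken only after the extraction would mix in extraction pain. This stands: the existing scores should be kept and their timing is correct. A reader might infer that the pain comparison is mis-measured; the documents do not support that.

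Second, clinical success occurs only in a heading and in neither statement of the aim. This also stands. It is a loose promise, not a broken endpoint.

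Third, inadequate anesthesia is to be recorded for both systems, so it would be wrong to say that such data exist for one device only. This stands as to the listing. A criterion could also sit in data forms or an analysis plan not shown here. It does not remove the conflict with the Comfort-In-only exclusion, which is in the protocol itself.

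Fourth, a reader might infer that a jet which hurts less because it anesthetizes less would win. That is conjecture. No passage links injection pain to depth of anesthesia, and recognised Comfort-In failures are excluded, so they would not enter the pain comparison. Only partial or unrecognised failures could act in this way.

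Finally, the added outcome has little power for modest differences. That stands too, and is why it should be a secondary outcome.

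**Conclusion.** This is an inexpensive improvement, not an error in the injection-pain comparison. As written, the trial can compare injection pain. It cannot compare anesthetic success, because no score covers the extraction, the one relevant complication item has no criterion or time point, and such children are excluded on one side only. The Wong-Baker score should not be reported as postoperative pain.

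These statements rest on the protocol text alone. The exclusion counts and power figures rest on assumed failure rates, and the main power table also on independence within child. With 60 children, of the gaps examined under independence, only 30% v 5% reaches power above 0.9.

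**What to change.** 1. Keep the present FLACC and Wong-Baker scores, call them injection pain throughout, and give each one time point. Remove the label postoperative pain and the conflicting end-of-procedure timing.
2. Continue the same video through the extraction and score FLACC for that segment on both sides. Take a second Wong-Baker rating after the extraction on both sides.
3. Define inadequate anesthesia by one criterion and time point for both devices. Analyse it as a paired secondary outcome that counts every treated child, including those rescued. A rescued side counts as inadequate for the device first used; flag its extraction scores, since they then reflect the rescue injection as well.
4. Reconcile Section 2.2.3 (recording for both systems) with Section 4 (rescue and exclusion for Comfort-In only). How rescue is handled clinically is for the investigators; the statistical need is that these children's data stay in the data set.
5. Either define clinical success through item 3 or drop it from the heading of Section 2.2. State that injection pain will be interpreted together with this outcome.

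**Cost.** A few more minutes of video, one more faces rating per tooth, one line on each form and some scoring time, with no extra visit, staff or children. The extraction score also reflects handling of the tooth, which the within-child comparison largely balances. Power is limited unless the failure rates differ widely, so the paired difference should be reported with a confidence interval, and a non-significant test should not be read as equal success.
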